3. OBJECTIVES, ENDPOINTS, AND ESTIMANDS

Objectives	Endpoints	Estimands
Primary:	Primary:	Primary:

 To compare the efficacy of PF-07321332/ritonavir to placebo for the treatment of symptomatic COVID-19 in nonhospitalized adult participants with COVID-19 who are at low risk of progression to severe disease. 	
 Time (days) to sustained alleviation of all targeted COVID-19 signs/symptoms through Day 28. 	
 The difference in median time (days) to sustained alleviation of all targeted COVID-19 signs and symptoms through Day 28 between PF-07321332/ritonavir and placebo in nonhospitalized adult patients with COVID-19 who are at low risk of progression to severe disease at baseline and were treated ≤ 5 days after COVID-19 symptom onset. This will be estimated irrespective of adherence to randomized treatment.
Secondary:	Secondary:	Secondary:

 To describe the safety and tolerability of PF-07321332/ritonavir relative to placebo in the treatment of nonhospitalized symptomatic adult participants with COVID-19 who are at low risk of progression to severe disease. 	
 Incidence of TEAEs. Incidence of SAEs and AEs leading to discontinuations. 	
 Not Applicable.

 To compare PF-07321332/ritonavir versus placebo for COVID-19-related hospitalization and all-cause mortality in nonhospitalized adult participants with COVID-19 who are at low risk of progression to severe disease. 	
 Proportion of participants with COVID-19-related hospitalization or death from any cause through Day 28. Proportion of participants with death (all cause) through Week 24. 	
 The difference in proportions of patients experiencing COVID-19-related hospitalization or death from any cause through Day 28 in nonhospitalized adult patients with COVID-19 who are at low risk of progression to severe disease and were treated ≤ 5 days after COVID-19 symptom onset. This will be estimated without regard to adherence to randomized treatment. Not Applicable

 To compare PF-07321332/ritonavir versus placebo for COVID-19-related medical visits in nonhospitalized adult participants with COVID-19 who are at low risk of progression to severe disease. 	
 Number of COVID-19-related medical visits through Day 28. 	
 The difference in the estimated rate of the number of COVID-19-related medical visits through Day 28 in nonhospitalized adult patients with COVID-19 who are at low risk of progression to severe disease and were treated ≤ 5 days after COVID-19 symptom onset.

Objectives	Endpoints	Estimands
	
 Number of days in hospital and ICU stay in participants with COVID-19-related hospitalization through Day 28. 	
This will be estimated without regard to adherence to randomized treatment.
 
 The difference in the estimated rate of number of days in hospital and ICU stay in patients with COVID-19-related hospitalization through Day 28 in nonhospitalized adult patients with COVID-19 who are at low risk of progression to severe disease and were treated ≤ 5 days after COVID-19 symptom onset. This will be estimated without regard to adherence to randomized treatment.

 To compare PF-07321332/ritonavir to placebo for the duration and severity of signs and symptoms in nonhospitalized symptomatic adult participants with COVID-19 who are at low risk of progression to severe disease. 	
 Proportion of participants with severe signs/symptoms attributed to COVID-19 through Day 28. Time (days) to sustained resolution of all targeted COVID-19 signs/symptom through Day 28. Duration of each targeted COVID-19 sign/symptom. Progression to a worsening status in 1 or more self-reported COVID-19-associated symptoms through Day 28. Proportion of participants with a resting peripheral oxygen saturation $\geq 95\%$ at Days 1 and 5. 	
 Not Applicable.

 To determine the PK of PF-07321332 in nonhospitalized adult participants with COVID-19 who are at low risk of progression to severe disease. 	
 PF-07321332 PK in plasma and whole blood (if feasible). 	
 Not Applicable.

 To describe the viral load in nasal samples over time in nonhospitalized adult participants with COVID-19 who are at low risk of progression to severe disease. 	
 Viral titers measured via RT-PCR in NP/nasal swabs over time. 	
 Not Applicable.

4. STUDY DESIGN

4.1. Overall Design

This Phase 2/3, randomized, double-blind, placebo-controlled study in approximately 1980 symptomatic low risk participants with COVID-19 who are nonhospitalized will determine the efficacy, safety, and tolerability of PF-07321332/ritonavir compared with placebo. Eligible participants with a confirmed diagnosis of SARS-CoV-2 infection will be

randomized (1:1) to receive PF-07321332/ritonavir or placebo orally q12h for 5 days (10 doses total). Randomization will be stratified by geographic region, by vaccination status and by COVID-19 symptom onset (≤ 3 days vs > 3 to 5 days). Throughout the study period, provision will be made to allow study visits to be conducted at a participant's home or at another nonclinic location approved by the investigator where possible when participants are unwilling or unable to attend a clinic visit.

The total study duration is up to 24 weeks and includes a screening period of no more than 48 hours, administration of study intervention through Day 5 or Day 6, efficacy assessments through Day 28, a safety follow-up period through Day 34, and long-term follow up at Weeks 12 and 24.

An independent E-DMC will review unblinded data for this Study C4671002 to ensure the safety of participants throughout the duration of the study. In addition to up to weekly reviews of safety, the E-DMC will review the following:

- Sentinel cohort safety review: The E-DMC will review unblinded safety data after approximately the first 100 randomized participants have completed through Day 10. Whether enrollment is paused for this review will depend on the successful completion of the Study C4671005 sentinel cohort (after approximately the first 60 randomized participants have completed through Day 10). If the Study C4671005 sentinel cohort safety review has successfully completed and no clinically significant safety signals have been identified prior to enrollment of the first 100 participants in this Study C4671002, the study will continue without pause. Otherwise, enrollment of Study C4671002 will be paused pending the E-DMC review of safety data. After review of the sentinel cohort in this Study C4671002, the frequency of safety reviews may be reduced subsequently based on E-DMC recommendations.
- Proof-of-concept assessment: Viral load data when 25% (approximately 200 participants in the primary analysis set with evaluable data) complete the Day 5 assessments. Enrollment will not be paused during review of these data, but may be paused or stopped following E-DMC review.
- First interim analysis (45% planned enrollment through Protocol Amendment 4): A planned interim analysis for efficacy, futility and sample size reestimation was conducted after approximately 45% of participants completed the Day 28 assessments in the mITT analysis set.
- Second interim analysis (80% planned enrollment through Protocol Amendment 4): At the request of the E-DMC, a second interim analysis was conducted on 80% of enrolled participants without any adjustment to the alpha.

A third interim analysis (100% planned enrollment through Protocol Amendment 4) was performed on all participants enrolled through Protocol Amendment 4 and had completed the Day 34 visit. Data from the study are required to support regulatory submissions thereby necessitating this interim analysis.

Subsequent to the interim analyses above, there will be a final analysis for reporting the results of this study. The final study analysis will be performed after all participants have completed or otherwise withdrawn from the study.

4.2. Scientific Rationale for Study Design

This study evaluates safety and the potential effect of an investigational agent on alleviating/resolving COVID-19-associated symptoms, and on reducing the duration and severity of COVID-19-associated symptoms because participants are symptomatic upon entry to this study. In addition to symptoms, this study is also evaluating COVID-19-related hospitalization or death from any cause. Previous studies with mAbs directed against the SARS-CoV-2 spike (S) protein that have received an EUA from the US FDA showed efficacy in reducing SARS CoV-2 shedding on NP swabs and time to symptom resolution.²²⁻²⁴ Efficacy assessments (including participant reported COVID-19 symptoms and severity, and COVID-19 related medical visits) will be collected through Day 28. The symptom endpoint includes those recommended by FDA and relies on targeted symptoms that have been associated with COVID-19, and which are expected to be dynamic and improve with effective anti-SARS-CoV-2 therapy. NP/nasal swabs will be collected at specified timepoints to assess viral load over time.

This study uses a randomized, double-blind, placebo-controlled design, which is a well-accepted approach for evaluating efficacy in a clinical research setting. Randomization will be stratified by geographic region, by vaccination status and by COVID-19 symptom onset (≤ 3 days vs >3 to 5 days). An early safety analysis will be conducted following enrollment of approximately 100 participants. Placebo was selected as the comparator since as of this date there is no globally approved SoC treatment for this patient population.

Results from a protocol-specified 45% interim analysis of this study showed that the novel primary endpoint of self-reported, sustained alleviation of all symptoms for 4 consecutive days, as compared with placebo, was not met. In addition, the 45% interim analysis of the secondary endpoint of COVID-19-related hospitalization or death from any cause through Day 28 showed 0.6% of those who received PF-07321332/ritonavir were hospitalized following randomization (2 of 333 hospitalized with no deaths), compared with 2.4% of participants who received placebo and were hospitalized (8 of 329 hospitalized with no deaths). These secondary endpoint data demonstrate that treatment with PF-07321332/ritonavir may provide significant clinical benefit to patients at low risk of progression to severe COVID-19 as measured by the endpoint of hospitalization or death.

Furthermore, results from Study C4671005 showed PF-07321332/ritonavir treatment significantly reduced the risk of hospitalization or death from any cause by 89% compared with placebo in nonhospitalized symptomatic adult participants with COVID-19 who are at increased risk of progression to severe disease when they were treated within 3 days of symptom onset. In a secondary endpoint, PF-07321332/ritonavir treatment also reduced the risk of hospitalization or death from any cause by 88% compared with placebo in participants treated within 5 days of symptom onset. Therefore, data from Study C4671002 will be analyzed irrespective of whether participants begin treatment within 3 or 5 days of symptom onset.

4.2.1. Diversity of Study Population

Reasonable attempts will be made to enroll participants to ensure the study population is representative of the patient population that will be treated with PF-07321332/ritonavir in clinical practice.

4.2.2. Choice of Contraception/Barrier Requirements

Studies to evaluate the developmental toxicity of PF-07321332 have not been conducted. Therefore, the use of a highly effective method of contraception is required (see [Appendix 4](#)).

CCI [REDACTED]

4.3. Justification for Dose

A dosing regimen of 300 mg PF-07321332 coadministered with 100 mg ritonavir q12h administered orally for 5 days will be evaluated in this study. Dose selection for this study included consideration of all relevant available preclinical and clinical data, including repeat-dose toxicology studies, clinical safety, and PK data from the Phase 1 study (C4671001), and *in vitro* pharmacology studies with PF-07321332.

A preliminary population PK model was developed from the Phase 1 (C4671001) PK data. Following the first dose of 300 mg of PF-07321332 coadministered with 100 mg ritonavir q12h, median C_{trough} of unbound (free) PF-07321332 are predicted to be approximately 289 ng/mL (equivalent to 933 ng/mL total), ie, approximately 3-fold higher than the *in vitro* EC_{90} of 90.4 ng/mL determined in dNHBE cells (equivalent to 181 nM, f_u , human=0.310). At this dose, for a hypothetical intersubject variability of 60%, more than 95% of the participants are predicted to maintain free PF-07321332 concentrations above the *in vitro* EC_{90} over the 12- hour dosing interval.

The selected duration is based on the effectiveness demonstrated following 5 day administration of other antiviral agents used in the treatment of acute respiratory infections, such as remdesivir for SARS-CoV-2 and oseltamivir for influenza.

Preliminary safety data from Study C4671001, collected up to 07 April 2021 and 14 April 2021, showed an acceptable safety profile for single doses of PF-07321332 ranging from 150 mg to 1500 mg dosed alone and of 250 mg and 750 mg dosed with ritonavir (100 mg administered at -12h, 0h, 12h) and for 10 day repeated doses ranging from 75 mg BID to 500 mg BID with 100 mg ritonavir BID.

In Study C4671005, a dosing regimen of 300 mg PF-07321332 coadministered with 100 mg ritonavir q12h administered orally for 5 days was efficacious in reducing the incidence of COVID-19-related hospitalization or death from any cause in nonhospitalized symptomatic adult participants with COVID-19 who were at increased risk of progression to severe disease. PF-07321332 was safe and well tolerated.

The proposed dosing regimen of 300 mg PF-07321332 coadministered with 100 mg ritonavir q12h administered orally for 5 days is thus expected to be safe and efficacious.

4.4. End of Study Definition

The end of the study is defined as the date of the last visit of the last participant in the study shown in the [SoA](#) for the last participant in the trial globally.

A participant is considered to have completed the study if he/she has completed all periods of the study, including the last visit as shown in the [SoA](#).

5. STUDY POPULATION

This study can fulfill its objectives only if appropriate participants are enrolled including participants across diverse and representative racial and ethnic backgrounds. Use of a pre-screener for study recruitment purposes will include collection of information, that reflects the enrolment of a diverse participant population including, where permitted under local regulations, age, sex, and race, and ethnicity. The following eligibility criteria are designed to select participants for whom participation in the study is considered appropriate. All relevant medical and nonmedical conditions should be taken into consideration when deciding whether a particular participant is suitable for this protocol.

Prospective approval of protocol deviations to recruitment and enrollment criteria, also known as protocol waivers or exemptions, is not permitted.

5.1. Inclusion Criteria

Participants are eligible to be included in the study only if all of the following criteria apply:

Age and Sex:

1. Participants ≥ 18 years of age (or the minimum country-specific age of consent if >18) at the time of the Screening Visit.
 - WOCBP may be enrolled.
 - All fertile participants must agree to use a highly effective method of contraception. Refer to [Appendix 4](#) for reproductive criteria for male (Section [10.4.1](#)) and female (Section [10.4.2](#)) participants.

Type of Participant and Disease Characteristics:

2. Confirmed SARS-CoV-2 infection as determined by RT-PCR in any specimen collected within 5 days prior to randomization.

Note: RT-PCR is the preferred method; however, with evolving approaches to confirmation of SARS-CoV-2 infection, other molecular or antigen tests that detect viral RNA or protein are allowed. The test result must be available to confirm eligibility.

Participants may be enrolled based on positive results of a rapid SARS-CoV-2 antigen test performed at screening.

3. Initial onset of signs/symptoms attributable to COVID-19 within 5 days prior to the day of randomization and at least 1 of the specified signs/symptoms attributable to COVID-19 present on the day of randomization (see [Appendix 9](#) for criteria).
4. Participants who are willing and able to comply with all scheduled visits, treatment plan, laboratory tests, lifestyle considerations, and other study procedures.

Informed Consent:

5. Capable of giving signed informed consent as described in [Appendix 1](#), which includes compliance with the requirements and restrictions listed in the ICD and in this protocol.

5.2. Exclusion Criteria

Participants are excluded from the study if any of the following criteria apply:

Medical Conditions:

1. Has at least 1 characteristic or underlying medical condition (self-report is acceptable) associated with an increased risk of developing severe illness from COVID-19, including:
 - ≥ 65 years of age;
 - $BMI \geq 30$ kg/m²;
 - Current smoker (cigarette smoking within the past 30 days) and history of at least 100 lifetime cigarettes;
 - Chronic lung disease (if asthma, requires daily prescribed therapy);
 - Known diagnosis of hypertension;
 - CVD, defined as history of any of the following: myocardial infarction, stroke, TIA, HF, angina with prescribed nitroglycerin, CABG, PCI, carotid endarterectomy, and aortic bypass;
 - Type 1 or Type 2 diabetes mellitus;
 - CKD;
 - Sickle cell disease;
 - Neurodevelopmental disorders (eg, cerebral palsy, Down's syndrome) or other conditions that confer medical complexity (eg, genetic or metabolic syndromes and severe congenital anomalies);
 - Active cancer other than localized skin cancer, including those requiring treatment (including palliative treatment), as long as the treatment is not among the prohibited medications that must be administered/continued during the trial period;

- Medical-related technological dependence (eg, CPAP [not related to COVID-19]).
2. Immunosuppressive disease (eg, bone marrow or organ transplantation or primary immune deficiencies) OR prolonged use of immune-weakening medications:
 - Has received corticosteroids equivalent to prednisone ≥ 20 mg daily for at least 14 consecutive days within 30 days prior to study entry;
 - Has received treatment with biologics (eg, infliximab, ustekinumab, etc.), immunomodulators (eg, methotrexate, 6MP, azathioprine, etc), or cancer chemotherapy within 90 days prior to study entry’;
 - HIV infection with CD4+ cell count $< 200/\text{mm}^3$.
 3. History of hospitalization for the medical treatment of COVID-19.
 4. Current need for hospitalization or anticipated need for hospitalization within 48 hours after randomization in the clinical opinion of the site investigator (see Section 8.1.2).
 5. Prior to current disease episode, any confirmed SARS-CoV-2 infection, as determined by a molecular test (antigen or nucleic acid) from any specimen collection.
 6. Known medical history of active liver disease (other than nonalcoholic hepatic steatosis), including chronic or active hepatitis B or C infection, primary biliary cirrhosis, Child-Pugh Class B or C or acute liver failure.
 7. Receiving dialysis or have known renal impairment.
 8. Known HIV infection with viral load > 400 copies/mL or taking prohibited medications for HIV treatment (from known medical history within past 6 months of the screening visit) (Appendix 8).
 9. Suspected or confirmed concurrent active systemic infection other than COVID-19 that may interfere with the evaluation of response to the study intervention.
 10. Any comorbidity requiring hospitalization and/or surgery within 7 days prior to study entry, or that is considered life threatening within 30 days prior to study entry, as determined by the investigator.
 11. History of hypersensitivity or other contraindication to any of the components of the study intervention, as determined by the investigator.
 12. Other medical or psychiatric condition including recent (within the past year) or active suicidal ideation/behavior or laboratory abnormality that may increase the risk of study participation or, in the investigator’s judgment, make the participant inappropriate for the study.

Prior/Concomitant Therapy:

13. Current or expected use of any medications or substances that are highly dependent on CYP3A4 for clearance and for which elevated plasma concentrations may be associated

with serious and/or life-threatening events during treatment and for 4 days after the last dose of PF-07321332/ritonavir (see [Appendix 8](#)).

14. Concomitant use of any medications or substances that are strong inducers of CYP3A4 are prohibited within 28 days prior to first dose of PF-07321332/ritonavir and during study treatment (see [Appendix 8](#)).
15. Has received or is expected to receive monoclonal antibody treatment, antiviral treatment (eg, molnupiravir), or convalescent COVID-19 plasma.
16. Has received any SARS-CoV-2 vaccination within 12 months of screening.

Note: Participants entering the study must not receive any dose of a SARS-CoV-2 vaccine prior to Day 34.

Prior/Concurrent Clinical Study Experience:

17. Is unwilling to abstain from participating in another interventional clinical study with an investigational compound or device, including those for COVID-19 therapeutics, through the long-term follow-up visit. Previous administration with any investigational drug or vaccine within 30 days (or as determined by the local requirement) or 5 half-lives preceding the first dose of study intervention used in this study (whichever is longer).
18. Known prior participation in this trial or other trial involving PF-07321332.

Diagnostic Assessments:

19. Known history of any of the following abnormalities in clinical laboratory tests (within past 6 months of the screening visit):
 - AST or ALT level ≥ 2.5 X ULN;
 - Total bilirubin ≥ 2 X ULN (≥ 3 X ULN for Gilbert's syndrome);
 - eGFR < 45 mL/min/1.73 m² within 6 months of the screening visit, using the serum creatinine-based CKD-EPI formula;²⁸
 - Absolute neutrophil count < 1000 /mm³.

Note: If the investigator suspects the participant may have any of the above laboratory values, confirmatory tests should be performed at screening to confirm eligibility before the first dose of study intervention. See [Appendix 2](#) for more details.

20. Oxygen saturation of $< 92\%$ on room air obtained at rest within 24 hours prior to randomization.

NOTE: For a potential participant who regularly receives chronic supplementary oxygen for an underlying lung condition, oxygen saturation should be measured while on their standard home oxygen supplementation.

Other Exclusions:

21. Females who are pregnant or breastfeeding.
22. Investigator site staff or Pfizer employees directly involved in the conduct of the study, site staff otherwise supervised by the investigator, and their respective family members.

5.3. Lifestyle Considerations

5.3.1. Contraception

The investigator or his or her designee, in consultation with the participant, will confirm that the participant has selected an appropriate method of contraception for the individual participant and his or her partner(s) from the permitted list of contraception methods (see Section 10.4.4) and will confirm that the participant has been instructed in its consistent and correct use. At time points indicated in the SoA, the investigator or designee will inform the participant of the need to use highly effective contraception consistently and correctly and document the conversation and the participant's affirmation in the participant's chart (participants need to affirm their consistent and correct use of at least 1 of the selected methods of contraception) considering that their risk for pregnancy may have changed since the last visit. In addition, the investigator or designee will instruct the participant to call immediately if the selected contraception method is discontinued or if pregnancy is known or suspected in the participant or partner.

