Study intervention accountability				X		[X]		X			X [if needed]	
 Study intervention accountability is only performed at the Day 14 visit if the participant administered treatment after the Day 5 visit was conducted. If the Day 14 visit is not an in-person visit, study intervention accountability will then be performed during the Day 34 visit. See Section 6.4.
Contraception check		X		X	X	X	X	X			X	
 See Section 5.3.1.
Vital status check									X	X	X	
Long-term follow-up telemedicine interview									X	X		
 Staff will ask participants if they are experiencing COVID-19 signs and symptoms and conduct a vital status check.
CONCOMITANT TREATMENT(S)												
Prior/concomitant medications	X	X		X	X	X	X	X			X	
 All prescription and over-the-counter medications including vaccines taken by the participant within 30 days before study entry (considered prior treatment) will be recorded. Concomitant therapies will be collected through the Day 34 visit. Refer to Section 6.8.
Adjunctive therapeutic procedures	X	X		X	X	X	X	X			X	
 Will be collected through the Day 34 visit.
SERIOUS AND NONSERIOUS AE MONITORING	X	X	[X]	X	X	X	X	X			X	
 AEs should be assessed by means of a telemedicine visit if not feasible via an in-person visit. Refer to Section 8.3.

- Site staff should, in discussion with participants, determine the most appropriate location to conduct study visits, whether in-person or remotely by telemedicine. In-person visits should take place at the investigational site. If investigational site in-person visit is not feasible, then alternate venues may include the participant's home or an alternate, noninvestigational site location approved by the investigator. If an in-person visit is held at a location other than the investigational site, in certain situations the assigned HCP performing the visit may be unable to complete all assessments. In these cases, a telemedicine visit should also occur to perform the remaining assessments. Remote visits can be conducted using a telemedicine system approved for use at the site.
- Assessments indicated in brackets [X] will be performed only for in-person visits.

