10.4.2. Female Participant Reproductive Inclusion Criteria

A female participant is eligible to participate if she is not pregnant or breastfeeding, and at least 1 of the following conditions applies:

- Is not a WOCBP (see definitions below in Section 10.4.3).

OR

- Is a WOCBP and using a contraceptive method that is highly effective (with a failure rate of <1% per year), as described below, during the intervention period and for at least 28 days after the last dose of study intervention, which corresponds to the time needed to eliminate any reproductive safety risk of the study intervention(s). If a highly effective method that is user dependent is chosen, a second effective method of contraception, as described below, must also be used. The investigator should evaluate the effectiveness of the contraceptive method in relationship to the first dose of study intervention.

Because ritonavir may reduce the effect of estradiol-containing contraceptives when agents are coadministered, a barrier method or other nonhormonal method of contraception must also be used if the participant is using estradiol-containing contraceptives.

The investigator is responsible for review of medical history, menstrual history, and recent sexual activity to decrease the risk for inclusion of a woman with an early undetected pregnancy.

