10.4.4. Contraception Methods

Contraceptive use by men or women should be consistent with local availability/regulations regarding the use of contraceptive methods for those participating in clinical trials.

1. Implantable progestogen-only hormone contraception associated with inhibition of ovulation.
2. Intrauterine device.
3. Intrauterine hormone releasing system.
4. Bilateral tubal occlusion (eg, bilateral tubal ligation).
5. Vasectomized partner:
 - A vasectomized partner is a highly effective contraceptive method provided that the partner is the sole sexual partner of the woman of childbearing potential and the absence of sperm has been confirmed. If not, an additional highly effective method of contraception should be used. The spermatogenesis cycle is approximately 90 days.
6. Combined (estrogen- and progestogen-containing) hormonal contraception associated with inhibition of ovulation:
 - Oral;
 - Intravaginal;
 - Transdermal.
7. Progestogen only hormone contraception associated with inhibition of ovulation:
 - Oral;
 - Injectable.
8. Sexual abstinence:
 - Sexual abstinence is considered a highly effective method only if defined as refraining from heterosexual intercourse during the entire period of risk associated with the study intervention. The reliability of sexual abstinence needs to be evaluated in relation to the duration of the study and the preferred and usual lifestyle of the participant.

In addition, one of the following effective barrier methods must also be used when option 6 or 7 are chosen above:

- Male or female condom with or without spermicide;
- Cervical cap, diaphragm, or sponge with spermicide;
- A combination of male condom with either cervical cap, diaphragm, or sponge with spermicide (double-barrier methods).

Because ritonavir may reduce the effect of estradiol-containing contraceptives when agents are co-administered, a barrier method or other nonhormonal method of contraception must also be used if the participant is using estradiol-containing contraceptives.

CCI [REDACTED]
[REDACTED]

| [REDACTED]

| [REDACTED]

| [REDACTED]

| [REDACTED]

| [REDACTED]

| [REDACTED]

| [REDACTED]

| [REDACTED]

[REDACTED]

10.6. Appendix 6: Liver Safety: Suggested Actions and Follow Up Assessments and Study Intervention Rechallenge Guidelines

Potential Cases of Drug Induced Liver Injury

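### The contraception affirmation charted under Protocol Section 5.3.1 covers one method, while Appendix 4 requires a second method for some women, so the Day 5, 10, 14 and 21 checks can be met after the required barrier has been stopped

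*Protocol*

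**What the plan says.** Protocol Section 5.3.1 has the investigator confirm an appropriate method "from the permitted list of contraception methods (see Section 10.4.4"), then at the Schedule of Activities time points remind the participant of the need for highly effective contraception and document both the conversation and an affirmation. The content of the affirmation is in a parenthesis: "participants need to affirm their consistent and correct use of at least 1 of the selected methods of contraception". Also, "the investigator or designee will instruct the participant to call immediately if the selected contraception method is discontinued".

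Appendix 4 sets the requirement itself:

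- Section 10.4.2, for women of childbearing potential: "If a highly effective method that is user dependent is chosen, a second effective method of contraception, as described below, must also be used". The period is "during the intervention period and for at least 28 days after the last dose of study intervention".
- Section 10.4.4, after the list of eight options: "In addition, one of the following effective barrier methods must also be used when option 6 or 7 are chosen above". Option 6 is combined hormonal contraception; option 7 is progestogen-only, oral or injectable.
- Sections 10.4.2 and 10.4.4, because ritonavir may weaken them: "a barrier method or other nonhormonal method of contraception must also be used if the participant is using estradiol-containing contraceptives".

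The "Contraception check" row of the Schedule of Activities marks Baseline, Days 5, 10, 14, 21 and 34, and early termination (ET). For content it refers only to Section 5.3.1.

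**The concern.** The routine check verifies less than the protocol requires. The plural in the Section 5.3.1 parenthesis allows for a participant with more than one selected method, yet sets the floor at one. For a woman on a pill plus barrier, continuing the pill alone satisfies the affirmation, and a correctly completed chart entry need not show that the barrier has stopped.

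What is at stake is participant safety. Section 4.2.2 says that developmental toxicity has not been studied and bases the contraception requirement on that. Appendix 4 adds the second method for estradiol-containing products because of an interaction with ritonavir. The check should be able to pick up loss of that second method.

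**Working it through.** No power, alpha or event figure is involved. The check sets the texts side by side and counts visits.

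**1. Required against affirmed**

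| Participant | Appendix 4 requires | Section 5.3.1 affirmation requires |
|---|---|---|
| Woman on option 6 or 7 | That method plus a barrier | One selected method |
| Woman on an estradiol-containing contraceptive | That method plus a barrier or other nonhormonal method | One selected method |
| Woman on a user-dependent highly effective method (10.4.2) | That method plus a second effective method | One selected method |
| Woman with an implant or intrauterine device | That method | One selected method |
| Man using a condom | Condom; a partner's method is optional (10.4.1) | One selected method |

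The two columns differ in the first three rows. The list in 10.4.4 does not label which options are user dependent. Its explicit barrier rule names options 6 and 7, which is 2 of 8.

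**2. Checks per participant**

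Baseline (1) + Days 5, 10, 14 and 21 (4) + Day 34 or ET (1) = at most 6. ET is defined as prior to Day 34, so it replaces that visit.

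**3. Are the mid-study checks inside the required period?**

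- Latest Day 21 check, with the 2-day window: 21 + 2 = Day 23.
- Earliest end of the required period after a full course: 5 + 28 = Day 33, or 6 + 28 = Day 34 when only one dose was taken on Day 1.
- Shortest case, dosing on Day 1 only: 1 + 28 = Day 29.
- Day 23 is before Day 29, so all 4 checks (Days 5, 10, 14 and 21) fall inside the period in every case.

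**4. Does another provision cover these four visits?**

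- *Selection from the 10.4.4 list.* This applies when a method is chosen and does not alter what is affirmed later.
- *The reminder.* It concerns highly effective contraception. Appendix 4 calls the added barrier an effective method, so the reminder does not name it.
- *The call instruction.* It refers to a single selected method and depends on the participant calling.
- *Section 8.2.6.* It asks staff to confirm adherence to every method the protocol requires, but in the paragraph on home pregnancy testing. Tests are scheduled only at screening and at Day 34 or ET, with extra tests for a missed cycle or suspected pregnancy. Scheduled tests at Days 5, 10, 14 and 21: 0.

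None of the four changes the content of the affirmation at those visits.

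**The case against.** The strongest reply is that nothing conflicts. Section 5.3.1 covers every fertile participant, including men using condoms and women for whom an implant or intrauterine device suffices. A floor that fits everyone does not contradict an extra rule for some. Staff must also chart the conversation, and the method must come from a section that carries the barrier rule, so a careful site would reach the two-method requirement. The replacement affirmation would still be self-report, and the Day 10 and Day 21 visits are by telemedicine by default.

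Much of this stands. A reader might infer that Section 5.3.1 relaxes Appendix 4 or permits dropping the barrier. The documents do not support that: the Appendix 4 rules are mandatory and nothing in 5.3.1 waives them. Nor is the affirmation the only thing charted. What remains is that the one item whose content is prescribed is set below the protocol's own requirement. A careful site may ask about the barrier, but the stated standard does not make it do so. Self-report limits any such check, but asking about every required method elicits more than asking about one.

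Appendix 8 complicates the picture for ethinyl estradiol. It is listed among the prohibited medications, from the first dose through 4 days after the last (5 + 4 = Day 9, or 6 + 4 = Day 10, after a full course), with a comment that an added nonhormonal method be considered. Section 6.8 and option 6 in 10.4.4 allow hormonal contraceptives. Read strictly, a woman still taking ethinyl estradiol at the Day 5 check during a full course, and possibly at the Day 10 check (Days 9 to 11 with its window), already breaches Appendix 8. The four visits are therefore not alike for her. That conflict is separate and does not remove the gap: the later checks remain, and option 7 contains no estrogen.

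**Conclusion.** The point holds as a minor verification gap. For women whose method needs a second one under Appendix 4, the charted affirmation can be truthful after the barrier has been stopped, at up to four scheduled checks inside the required period. Appendix 4 remains binding throughout.

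The count is of visits and listed options. The documents give neither the number of women using these methods nor how often a barrier is abandoned, so a reader who infers a quantified pregnancy risk goes beyond them. The conclusion assumes that sites apply the affirmation as worded and attend the scheduled visits within their windows. No endpoint, estimand or analysis is affected.

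**What to change.** In Section 5.3.1, replace "participants need to affirm their consistent and correct use of at least 1 of the selected methods of contraception" with: *participants need to affirm their consistent and correct use of all methods of contraception required for that participant under Section 10.4 (Appendix 4)*. Have the existing chart entry name each method affirmed. Participants who need only one method would still affirm one.

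The cost is one phrase and a more specific entry in a record already required. No visit, test or form is added.

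The ethinyl estradiol comment in Appendix 8 should not be edited alone, because stricter wording there would tell sites how to use a drug that the same table prohibits. If Appendix 8 is opened, first resolve the conflict with Section 6.8 and option 6 in 10.4.4: move the row out of the prohibited table and state that a barrier or other nonhormonal method is mandatory with it.
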